12. SIZE OF THE STUDY AND EVALUTION

The 12 to 15 year follow-up of 80,000 women should result in about 620,000 documented women-years. This estimate is based on the assumptions that (1) ZEG's physicians' network could recruit 80,000 women within three years, and (2) the annual drop-out rate is less than 10% (based on the EURAS-OC [1] and LASS studies: 10% for FU years 1-5, 7% for FU years 6-10, and 5% for FU years 11+). Details for 36-months recruitment scenario are given in Table 1a and 1b: Table 1a based on the assumption that the follow-up period is max. 15 years, Table 1b calculates the observation time with extending the follow-up period by one year (and therefore increasing the number of women-years).

Table 1a: Expected observation time (max. 15 years follow-up): Patient recruitment within 3 years (annual recruitment rate = 26,667 women)

Time (y)*	Sub-cohorts recruited during the					
	1 st study year		2 nd study year		3 rd study year	
	No. of women	Time of observation	No. of women	Time of observation	No. of women	Time of observation
1	25,310	12,913				
2	22,779	24,045	25,310	12,913		
3	20,501	21,640	22,779	24,045	25,310	12,913
4	18,451	19,476	20,501	21,640	22,779	24,045
5	16,606	17,529	18,451	19,476	20,501	21,640
6	15,444	16,025	16,606	17,529	18,451	19,476
7	14,363	14,903	15,444	16,025	16,606	17,529
8	13,357	13,860	14,363	14,903	15,444	16,025
9	12,422	12,890	13,357	13,860	14,363	14,903
10	11,553	11,987	12,422	12,890	13,357	13,860
11	10,975	11,264	11,553	11,987	12,422	12,890
12	10,426	10,701	10,975	11,264	11,553	11,987
13	9,905	10,166	10,426	10,701	10,975	11,264
14	9,410	9,657	9,905	10,166	10,426	10,701
15	8,939	9,174	9,410	9,657	9,905	10,166
WY (total)		216,230		207,056		197,398
WY (grand total)	620,684					

* Time after start of recruitment

** The number of recruited women equals 26,667. However, the number of women at the end of the first year is lower because some women will drop out during the first year (daily drop-out rate for follow-up years 1-5: ~ 0.029%, for years 6-10: ~ 0.020%, for years 11+: ~ 0.014%).

Table 1b: Expected observation time (alternative of extending the follow-up by one year): Patient recruitment within 3 years (annual recruitment rate = 26,667 women)

Time (y)*	Sub-cohorts recruited during the					
	1 st study year		2 nd study year		3 rd study year	
	No. of women	Time of observation	No. of women	Time of observation	No. of women	Time of observation
1	25,310	12,913				
2	22,779	24,045	25,310	12,913		
3	20,501	21,640	22,779	24,045	25,310	12,913
4	18,451	19,476	20,501	21,640	22,779	24,045
5	16,606	17,529	18,451	19,476	20,501	21,640
6	15,444	16,025	16,606	17,529	18,451	19,476
7	14,363	14,903	15,444	16,025	16,606	17,529
8	13,357	13,860	14,363	14,903	15,444	16,025
9	12,422	12,890	13,357	13,860	14,363	14,903
10	11,553	11,987	12,422	12,890	13,357	13,860
11	10,975	11,264	11,553	11,987	12,422	12,890
12	10,426	10,701	10,975	11,264	11,553	11,987
13	9,905	10,166	10,426	10,701	10,975	11,264
14	9,410	9,657	9,905	10,166	10,426	10,701
15	8,939	9,174	9,410	9,657	9,905	10,166
16	8,492	8,716	8,939	9,174	9,410	9,657
WY (total)		224,946		216,230		207,056
WY (grand total)	648,232					

* Time after start of recruitment

** The number of recruited women equals 26,667. However, the number of women at the end of the first year is lower because some women will drop out during the first year (daily drop-out rate for follow-up years 1-5: ~ 0.029%, for years 6-10: ~ 0.020%, for years 11+: ~ 0.014%).

Overall, it is expected that the observation time in the study will be in the range of 620,000 WY (up to 15 years of follow-up) and 650,000 WY (up to 16 years of follow-up).

Evaluation part I

An evaluation of the cardiovascular events will take place 5 years after study start. In Table 2 are the total women-years shown which will be observed at that point in time. Based on the results of EURAS-OC [1], it is assumed that at that point in time about 4/5 of the observed time represents exposure time. Therefore, 232,000WY will result in approx. 185,000WY of OC exposure 5 years after study start.

Table 2: Expected observation time for cardiovascular risk (5 years): Patient recruitment within 3 years (annual recruitment rate = 26,667 women)

Time (y)*	Sub-cohorts recruited during the					
	1 st study year		2 nd study year		3 rd study year	
	No. of women	Time of observation	No. of women	Time of observation	No. of women	Time of observation
1	25,310	12,912				
2	22,779	24,044	25,310	12,913		
3	20,501	21,640	22,779	24,045	25,310	12,913
4	18,451	19,476	20,501	21,640	22,779	24,045
5	16,606	17,528	18,451	19,476	20,501	21,640
WY (total)		95,600		78,074		58,598
WY (grand total)	232,272					

* Time after start of recruitment

** The number of recruited women equals 26,667. However, the number of women at the end of the first year is lower because some women will drop out during the first year (daily drop-out rate ~ 0.029%).

The study was designed to analyze rare and very rare events (according to the CIOMS classification 1 – 10 and less than 1 event(s) per 10,000 women-years, respectively). The adverse events of particular interest for the sample size calculation are VTE, ATE and colorectal cancer. Based on the EURAS-OC results (see section 1) the estimated VTE and ATE incidence rates in the young study population are ~9/10,000WY for VTE and ~2/10,000WY for ATE. However, in the DRSP/EE cohort, a reduced incidence for ATE (<1/10,000WY) was observed. Since the EURAS-OC results are the most reliable and comparable data available, further calculations are based on these results. For colorectal cancer the expected incidence is 0.65/10,000WY based on the CancerMPact database, which is the best source to derive incidence rates for colorectal cancer in certain sub-populations. Based on this incidence, the following sample size was calculated; in case the study shows other

incidence rates at a later point in time, a re-calculation might be necessary and has to be discussed with the Safety Monitoring and Advisory Council.

The COC+ cohort consists of several newly marketed products and for this combined cohort a proportion of 25-35% of the total study population seems to be realistic. Furthermore it is assumed that the proportion for the individual products will be in the range of 7-12%. Power calculations based on the incidences given above showed that approximately 110,000 to 180,000WY would be needed to show non-inferiority of individual COC+ products versus established OCs for VTE. The calculations for VTE are based on the assumptions given in Table 3. In essence, the study is powered to exclude a twofold risk of VTE for the DRSP/EE+ cohort (primary variable) as well as for folate-containing products with at least 7% of the total exposure – if the true risk of VTE is not different for the individual (sub)-cohorts.

Table 3: Power calculation³² for VTE based on the assumption that the true incidence in the relevant COC+ (sub)-cohort is not different from the reference cohort.

Test significance level, α (one-sided)	0.025 (= 0.05 two-sided)	
VTE Incidence for reference cohort	9/10,000 WY	
Non-inferiority margin	9/10,000 WY (equal to the VTE incidence for the reference cohort)	
Expected VTE incidence for COC+ cohort	9/10,000 WY	
Power (%)	90	
Proportion of COC+ users (% of study population)	7	12
Required women years in COC+ cohort	12,543	13,256
Required women years in reference cohort	166,635	97,204
Total women years	179,178	110,460

Furthermore, 124,000 to 172,000WY of exposure would be sufficient to also exclude a twofold risk for ATE (cf. Table 4), assuming that 1) the incidence for DRSP/EE+ is comparable to the EURAS-OC results (~ 1/10,000) and 2) DRSP/EE+ accounts for at least 8% of the total exposure.

Table 4: Power calculation³² for ATE based on the assumption that the true incidence in the DRSP/EE+ cohort is ~ 1/10,000 compared to ~ 2/10,000 in the reference cohort.

Test significance level, α (one-sided)	0.025 (= 0.05 two-sided)	
ATE Incidence for reference cohort	2/10,000 WY	
Non-inferiority margin	2/10,000 WY (equal to twice the ATE incidence for the reference cohort)	
Expected ATE incidence for DRSP/EE+ cohort	1/10,000 WY	
Power (%)	90	
Proportion of DRSP/EE+ users (% of study population)	8	12
Required women years in DRSP/EE+ cohort	13,704	14,858
Required women years in reference cohort	157,594	108,953
Total women years	171,298	123,811

Evaluation Part II

For the primary outcome of interest (VTE/ATE), 90% power is taken as a basis. For the additional outcome of interest (colorectal cancer), a power reduction to 80% is also acceptable.

Power calculations for colorectal cancer are based on an incidence rate of 0.65/10,000WY. As a potential risk for colorectal cancer is associated with folate and not progestogen/estrogen combinations, the assessment of colorectal cancer will be based primarily on the combined COC+ cohort. For this cohort a proportion of 25-35% of the total study population is expected (see above). Based on a proportion of 35% and 25% approx. 531,000 and 644,000 WY of observation, respectively, are needed to exclude a two-fold risk of colorectal cancer (cf. Table 5). i.e., if the proportion should be 25%, it might be necessary to extend the follow-up period by one year as proposed in Table 1b. The final decision on the timely line of the INAS-FOCUS study should be made by the Safety Monitoring and Advisory Council after analysis of the incidence data within this study and discussion of the appropriate measures.

Table 5: Power calculation^{32 33} for colorectal cancer based on the assumption that the true incidence in the COC+ cohort is not different from the reference cohort.

Test significance level, α (one-sided)	0.025 (= 0.05 two-sided)	
Colorectal cancer incidence for reference cohort	0.65/10,000WY	
Non-inferiority margin	0.65/10,000WY (equal to the colorectal cancer incidence for the reference cohort)	
Expected colorectal cancer incidence for COC+ cohort	0.65/10,000WY	
Power (%)	80	
Proportion of COC+ users (% of study population)	25	35
Required women years in COC+ cohort	160,993	185,761
Required women years in reference cohort	482,977	344,984
Total women years	643,970	530,745

These power calculations suggest that this study is sufficiently powered to show non-inferiority of COC+ compared to established OCs. However, exact power calculations based on actual incidences and drop-out rates should be done on the basis of two years follow-up data. If these calculations do not confirm the assumed incidences and drop-out rates the independent Safety Monitoring and Advisory Council (SMAC) may discuss the need for adapting patient numbers and follow-up times.

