7. FOLLOW-UP

A follow-up assessment for each woman is scheduled 6, 12, 18, 24 months after baseline, and then 3, 4, 5, 7½, 10, 12½, 15 years after recruitment. Women will be followed-up for at least 12 years. Women recruited in the early phase of the study will be followed-up until study endpoint [max. 15 years]. During Part II of the study (cf. Section 12) women will be followed-up at 2 ½ yearly intervals. Based on investigator experience from other long-term studies, women who remain in the study for 5 years are likely to remain in the study, even if follow-up periods extend beyond one year.

Follow-up questionnaires will be mailed to the participating women, who often know more about their own personal health related issues than the physician who prescribes their OC. This is especially true for potential adverse events treated by other

physicians. Occasionally, events may be reported by the participant or by a participant's relatives, friends or attending physicians between the regular follow-ups. These reports will be documented and validated in the same way as regular reports (see section 8).

In addition to the follow-up questionnaires, at the 18-month follow-up, a validated food-frequency questionnaire (Dietary Folate Equivalents (DFE) screener) specific for folate intake will be sent to study participants. Folate intake has a relatively stable intra-person variability, particularly in individuals consuming a western diet. In contrast, inter-person variability tends to vary significantly. A single DFE screener during the follow-up period will rank individuals in regard to their average dietary folate intake (inter-person variability) and provide sufficient information for analysis purposes. The DFE is a validated and widely used methodology for capturing micronutrient data in large populations and can be tailored for individual countries. It is expected that women use OCs for an average of approx. 3 to 4 years. Follow-up at 18 months would therefore be a good predictor of folate intake during OC use.

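### Tables 1a and 1b apply the lower drop-out rates half a year too early, which removes the reserve of the one-year extension at a 25% COC+ share; how much of the total is documented depends on a drop-out date the protocol does not define

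*Protocol*

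**What the plan says.** Section 12 of the protocol expects that follow-up of 80,000 women "should result in about 620,000 documented women-years". It repeats the figure after Table 1b: "it is expected that the observation time in the study will be in the range of 620,000 WY", rising to 650,000 with one more year.

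The inputs are three yearly sub-cohorts ("annual recruitment rate = 26,667 women") and annual drop-out of "10% for FU years 1-5, 7% for FU years 6-10, and 5% for FU years 11" and later. A table footnote gives these as percentages per day ("daily drop-out rate for follow-up years 1-5: ~ 0.029%, for years 6-10: ~ 0.020%, for years 11+: ~ 0.014"). The table rows, however, count years since recruitment opened.

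Section 7 schedules questionnaires at 6, 12, 18 and 24 months, "and then 3, 4, 5, 7½, 10, 12½, 15 years after recruitment". In Part II, "women will be followed-up at 2 ½ yearly intervals".

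Table 5 requires 643,970 WY at a 25% COC+ share and 530,745 WY at 35%, for 80% power on colorectal cancer. For the 25% case, Evaluation Part II says "it might be necessary to extend the follow-up period by one year as proposed in Table 1b".

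**The concern.** There are two separate issues.

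**Timing of the rates.** Section 12 ties the 10%, 7% and 5% rates to follow-up years. The tables tie them to years since the start of each sub-cohort's recruitment year. Women enter throughout that year, so they are on average half a year behind the row number. The lower rates therefore start too early and the totals come out too high.

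**What counts as documented.** A daily drop-out rate with averaged head-counts credits a woman up to the day she leaves. If she leaves between questionnaires, the plan gives no systematic information on her health after the last one she returned. In Part II that gap can approach 2½ years.

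At stake is the colorectal cancer evaluation at the low end of the protocol's own 25-35% range. There the remedy is Table 1b, whose reserve over Table 5 is 648,232 − 643,970 = 4,262 WY, or 0.66%.

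**Working it through.** **1. Reproducing the stated totals.** Uniform entry over one year with annual retention 0.90 leaves 25,310 of 26,667 women at the end of year 1, as stated. Start from 25,310 women and the stated 12,913 WY. In each later row multiply the women by (1 − d) and take the mean of the start and end counts as the time. With d = 10% for rows 2-5, 7% for rows 6-10 and 5% from row 11, this gives 620,677 WY (stated 620,684) and 648,224 WY (stated 648,232).

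**2. The timing error in the rows.** In the first sub-cohort 16,606 × 0.93 = 15,444, so 7% is applied throughout row 6. At the start of row 6 these women have 4 to 5 years of follow-up, and on average they complete year 5 only halfway through the row. The same happens at row 11 (11,553 × 0.95 = 10,975), and in all three sub-cohorts.

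**3. Hand check of the size, from Table 1b's own rows.** Half a year more at 10% instead of 7% lowers rows 7-11 by at least 1 − √(0.90/0.93) = 1.626%. After the second step, the rows from 12 on are lowered by 1 − √(0.90/0.95) = 2.667%.

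- Rows 7-11: (14,903 + 13,860 + 12,890 + 11,987 + 11,264) = 64,904 WY per sub-cohort; × 3 × 0.01626 ≈ 3,166 WY.
- Rows 12 on: 48,414 + 39,698 + 30,524 = 118,636 WY over the three sub-cohorts; × 0.02667 ≈ 3,164 WY.

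Together that is about 6,330 WY, without counting row 6. It already exceeds the reserve of 4,262 WY.

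**4. Full calculation.** Entry is uniform over three years, drop-out is exponential at 10/7/5% by each woman's own follow-up year, and time is integrated to the data cut. The last-contact variants use WY = sum over intervals of (interval length × retention to the contact that closes it), with contacts at 0.5, 1, 1.5, 2, 3, 4, 5, 7.5, 10, 12.5 and 15 years.

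| Basis | Year 15 | Year 16 | Change from stated |
|---|---|---|---|
| Stated (Tables 1a, 1b) | 620,684 | 648,232 | |
| Timing corrected, drop-outs credited to day of leaving | 613,790 | 640,587 | −1.1%, −1.2% |
| Also drop-outs credited to last contact, retained women to a close-out contact | 578,070 | 603,242 | −6.9%, −6.9% |
| Same, no close-out contact | 539,436 | 572,672 | −13.1%, −11.7% |

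Continuous integration with the tables' own timing gives 620,219 and 647,760. The timing effect itself is therefore 6,429 and 7,173 WY. Taken from the stated 648,232, it leaves 641,059 WY, still below 643,970. With the tables' timing kept, last-contact crediting alone (with close-out) gives 585,351 and 611,221, about 5.6% less than 620,219 and 647,760.

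**5. Power by Table 5's method.** With equal rates λ = 0.65/10,000, margin λ and share p, the required total is (1.960 + 0.842)² × (1 − λ) / [λ p(1 − p)]. This gives 643,969 at 25% (stated 643,970) and 530,745 at 35% (as stated). Power at total T is Φ(√[λ T p(1 − p)] − 1.960). At 25% and year 16:

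- T = 640,587: √7.807 = 2.794, power 79.8%.
- T = 603,242: √7.352 = 2.711, power 77.4%.
- T = 572,672: √6.979 = 2.642, power 75.2%.

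Solving p(1 − p) = 7.849/(λT) for 80% power at year 16 gives minimum shares of 25.2%, 27.7% and 30.2%. At 35% the requirement of 530,745 WY is met in every row of the table, even at year 15 (539,436).

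**The case against.** **The drop-out date is undefined.** The rates come from earlier cohorts. If those cohorts dated leaving at last contact, the curve already ends where documentation ends, and cutting back again would double-count. This stands: the documents do not settle it, and in that case only the timing correction remains.

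**Not every drop-out is a silent loss.** Section 7 accepts occasional reports between questionnaires, describes four levels of tracing, and aims for loss to follow-up below 5% in Europe and 10% in the US. That is at most 1,500 + 5,000 = 6,500 women, against about 54,000 drop-outs by year 16 under the stated rates. If only those 6,500 were undated, at a mean loss of 0.68 years each, about 4,400 WY (0.7%) would go. This too is an assumption, but it shows that the full cut is not forced. On the other side, the death-register search is optional and clarifies vital status, not cancer incidence.

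**The protocol hedges and re-checks.** A reader might infer that it promises one extra year to be enough. It says only that an extension might be necessary, leaves the timeline to the SMAC, and plans power calculations on two-year data. That stands. But the two-year check precedes follow-up years 6 and 11 and every 2½-year interval, so it does not repair the table method.

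**The loss is confined to the low shares.** At a 30% share Table 5's method needs 574,972 WY, which 578,070 at year 15 would meet if there is a close-out contact. This also stands.

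**Conclusion.** The timing error follows from the protocol alone. The totals should be about 613,800 and 640,600 WY, and at a 25% share the one-year extension does not reach 643,970 WY. Taken alone this costs 0.2 points of power against the 80% target; what matters is that the stated reserve does not exist.

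The loss from crediting drop-outs beyond their last contact is conditional. With last-contact crediting and a close-out contact, the totals are about 578,000 and 603,000 WY, with about 77% power at 25% and year 16. Without a close-out contact they are about 539,000 and 573,000 WY, with about 75% power. If drop-out is already dated at last contact, nothing is added to the timing correction.

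A reader might take the 7% reduction as an established overstatement. The documents do not support that: it is one scenario in a range of about 1% to 13%, and it combines the timing effect with two conventions the protocol does not state. Nor do the documents support the inference that the colorectal cancer evaluation fails as a whole, since the 35% scenario is met in every variant.

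**What to change.** - Recompute Tables 1a and 1b with the drop-out rates applied by each woman's own follow-up year.
- State the date at which a drop-out is censored, and whether a close-out contact is made at the data cut.
- Replace the 620,000 and 650,000 WY by the resulting figures, given as a range where the convention stays open.
- In Evaluation Part II, state that at a 25% share the one-year extension does not reach 643,970 WY. Give the achieved power: about 77-80% if a close-out contact is made, about 75% if not. Alternatively give the minimum COC+ share at year 16: up to about 28% with a close-out contact, about 30% without.

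The cost is two recalculated tables and a few sentences. No additional women are needed. A close-out contact would be extra work only if the sponsor chooses to add one. The stated figures become slightly less favourable.

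### Table 4's 90% power to exclude a twofold ATE risk for DRSP/EE+ rests on about 1.4 expected events and is not reached on the hazard-ratio scale the protocol uses

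*Protocol*

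**What the plan says.** Section 12 (Evaluation part I) claims that "124,000 to 172,000WY of exposure would be sufficient to also exclude a twofold risk for ATE". The sentence carries two conditions: a DRSP/EE+ rate of about 1 per 10,000 women-years (WY), and that "DRSP/EE+ accounts for at least 8% of the total exposure".

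The source of the lower rate is an earlier cohort study, where "in the DRSP/EE cohort, a reduced incidence for ATE (<1/10,000WY) was observed". Table 4's title repeats that the "true incidence in the DRSP/EE+ cohort is ~ 1/10,000 compared to ~ 2/10,000 in the reference cohort".

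Table 4 sets one-sided alpha at 0.025 and power at 90%. It describes the margin as "2/10,000 WY (equal to twice the ATE incidence for the reference cohort". It requires 13,704 DRSP/EE+ and 157,594 reference WY at an 8% share (171,298 in total), or 14,858 and 108,953 at 12% (123,811 in total). It shows no expected event counts.

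Evaluation Part II adds: "For the primary outcome of interest (VTE/ATE), 90% power is taken as a basis". Section 11 names VTE alone as the primary variable. There the upper confidence limit of a hazard ratio is compared with 2, using Cox models, and similar analyses are announced for ATE.

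**The concern.** Three features of Table 4 do not fit the rest of the plan.

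- **Assumed benefit.** Tables 3 (VTE) and 5 (colorectal cancer) assume equal rates. Table 4 alone assumes that the test product halves the risk. This widens the distance to be detected from 2 to 3 per 10,000.
- **Very few events.** The formula relies on a normal approximation, yet the required DRSP/EE+ exposure yields between one and two events.
- **Scale.** Table 4 is sized on a rate difference, while section 11 concludes on a hazard ratio against 2.

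AMI and cerebrovascular accidents are main outcomes, and ATE is evaluated five years after study start. If the 90% figure stands, an ATE comparison that cannot exclude a doubling may be read as coming from a well-powered study.

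**Working it through.** **Inputs (Protocol, section 12).** r1 = 1/10,000 (DRSP/EE+), r0 = 2/10,000 (reference), margin d = 2/10,000, one-sided alpha 0.025, power 90%. DRSP/EE+ share is 8% or 12%, so k (reference to DRSP/EE+ exposure) = 11.5 or 7.33. Exposure expected at five years is about 185,000 WY.

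**1. Reproducing Table 4.** WY(DRSP/EE+) = (1.960 + 1.282)² × (r1 + r0/k) / (d + r0 − r1)².

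- 8%: 10.507 × (0.0001 + 0.0002/11.5) / 0.0003² ≈ 13,705
- 12%: 10.507 × (0.0001 + 0.0002/7.33) / 0.0003² ≈ 14,859

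With the binomial variance r(1 − r) these become 13,704 and 14,858, as printed.

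**2. Expected events.** DRSP/EE+: 13,704 × 0.0001 = 1.37 and 14,858 × 0.0001 = 1.49. Reference: 157,594 × 0.0002 = 31.5 and 108,953 × 0.0002 = 21.8. The chance of no DRSP/EE+ event is exp(−1.37) = 25% and exp(−1.49) = 23%.

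**3. Table 4's own test.** I summed independent Poisson counts over all outcomes where the upper limit of the rate difference, x/W1 − y/W0 + 1.96√(x/W1² + y/W0²), lies below d. Power is 81.8% (8%) and 81.3% (12%). At a true twofold risk the test passes 8.5% and 7.3% of the time, not 2.5%.

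**4. Hazard-ratio scale.** The formula is power = Φ(ln(2/HR)/SE − 1.96), with SE = √(1/e1 + 1/e0) and e1, e0 the expected events. At HR = 0.5:

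- 8%: SE = √(1/1.37 + 1/31.5) = 0.873; Φ(1.386/0.873 − 1.96) = 35.5%
- 12%: SE = 0.848; power 37.3%

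I then enumerated three ways to test HR ≥ 2. Exact: P(X ≤ x) ≤ 0.025 for X ~ Binomial(n, p0), with n total events and p0 = 2·W1/(2·W1 + W0). Likelihood ratio: x/n < p0 and the binomial statistic exceeds 3.84. Wald: upper limit of the log rate ratio below ln 2, with zero DRSP/EE+ events counted as failure.

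| WY, DRSP/EE+ / reference | True HR | Expected events | Exact | Likelihood ratio | Wald |
|---|---|---|---|---|---|
| 13,704 / 157,594 | 0.5 | 1.37 / 31.5 | 34% | 57% | 2% |
| 14,858 / 108,953 | 0.5 | 1.49 / 21.8 | 37% | 57% | 6% |
| 14,800 / 170,200 (8% of 185,000) | 0.5 | 1.48 / 34.0 | 39% | 60% | 4% |
| 22,200 / 162,800 (12% of 185,000) | 0.5 | 2.22 / 32.6 | 63% | 75% | 44% |
| 13,704 / 157,594 | 1 | 2.74 / 31.5 | 12% | 24% | 1% |
| 14,858 / 108,953 | 1 | 2.97 / 21.8 | 13% | 25% | 3% |
| 14,800 / 170,200 | 1 | 2.96 / 34.0 | 13% | 26% | 2% |
| 22,200 / 162,800 | 1 | 4.44 / 32.6 | 23% | 33% | 19% |

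The exact test is conservative here (true error 1.1-1.5%); the likelihood-ratio test runs at about 3%.

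**5. Exposure needed.** With equal rates in the protocol's own formula:

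- 8%: 10.507 × (0.0002 + 0.0002/11.5) / 0.0002² ≈ 57,106 DRSP/EE+ WY; divided by 0.08, about 714,000 in total
- 12%: about 59,701; divided by 0.12, about 497,500 in total

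With the halved rate kept, the exact test reaches 90% at about 447,000 (8%) or 323,000 (12%) WY.

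**6. Margin label.** d = 2/10,000 is one times the reference rate. The tolerated DRSP/EE+ rate, 2 + 2 = 4 per 10,000, is twice it. Tables 3 and 5 label the same construction correctly.

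**The case against.** The best defence is that Table 4 is a correct calculation from a disclosed premise, and that stands. The women-years reproduce, the halved rate is given with its source, and the sufficiency sentence carries its conditions. A reader might infer an arithmetic error or a hidden assumption; the document supports neither. But disclosure does not rescue the 90%, because power falls short even when the halved rate is true.

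A reader might also infer that failure to exclude a doubling is close to certain. The document does not support that. It fixes no interval method, and near-certain failure holds only for Wald limits at Table 4 sizes or at an 8% share. With 22,200 DRSP/EE+ WY and 32.6 reference events, one or two DRSP/EE+ events give Wald upper limits of 1.65 and 1.88, both below 2. Zero events still yield a finite upper limit by exact or profile-likelihood methods.

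In the best planned case (185,000 WY, 12% share, halved rate) the difference test does reach 91% power, but with 6.2% one-sided error.

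Section 12 also foresees recalculating power after two years of follow-up. That addresses incidences and drop-out. It would not by itself resolve the mismatch of scale, the small-count approximation or the label. Finally, the formal hypotheses concern VTE only, so the study's primary test is not affected by this point.

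**Conclusion.** The point holds: the 90% power stated for ATE is not attained at the women-years said to be sufficient. Under the protocol's favourable rates, power on the hazard-ratio scale at Table 4 sizes runs from 2-6% to about 57% according to the interval method, with exact limits at 34-37%. All the exposure expected at five years raises exact power to 39-63% and likelihood-ratio power to 60-75%. Under equal rates, exact power does not exceed 23%.

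These figures assume constant Poisson rates, no covariate adjustment, the protocol's incidences and an 8-12% DRSP/EE+ share. They also take the announced similar analyses to mean that a hazard ratio is compared with 2 for ATE, as for VTE.

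It would go too far to conclude that the combined COC+ cohort should become the main ATE comparison. DRSP/EE+ is the primary objective and COC+ a secondary one. At 25-35% of 185,000 WY with equal rates, COC+ would itself reach only 41-48% exact power.

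**What to change.** In section 12:

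- Withdraw the statement that 124,000 to 172,000 WY suffice for ATE at 90% power.
- Restate ATE power on the hazard-ratio scale under both HR = 0.5 and HR = 1, next to the expected DRSP/EE+ events (about 1.5 to 2.2 at 185,000 WY under the assumed rate).
- Present ATE for DRSP/EE+ as an estimation outcome, with exact or profile-likelihood limits that remain defined at zero events.
- Keep the COC+ comparison for ATE as the secondary analysis already planned.
- Correct the margin label in Table 4: the value equals the reference incidence.

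No change to recruitment, follow-up or data collection is needed. The cost is protocol wording and a less favourable stated figure for ATE.
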